3.4. Simulation Study Objectives

The simulation study is beyond the scope of this SAP. It will be carried out by an external partner, Axtria. They will define their own statistical analysis.

Imperial Clinical Trials Unit	ZODIAC STATISTICAL ANALYSIS PLAN – MAIN ANALYSIS	V1 17 th Jan 2024
-------------------------------	--	------------------------------

4. Design

4.1. Study Design

An international, multicentre, cluster randomised, parallel arm trial with a total of 48 sites randomised to Standard of Care (SoC) [24 sites] or DSS [24 sites] across 3 countries: the United Kingdom (UK), Spain and Italy. There will be 16 sites per country; 8 DSS sites; 8 SoC sites. In the event of under-recruitment of sites in Italy or Spain, up to 6 replacement sites may be recruited from UK. DSS sites will receive a standardised period of training prior to commencing patient recruitment. Patients will be followed up for a maximum of 16 weeks. As there are no defined study visits after the patient's baseline visit all outcomes will be assessed as close to 16 weeks as possible.

4.2. Treatment Groups

Study sites will be allocated to either SoC group or the DSS group. Both groups will be following routine clinical care including local/national prescribing guidelines during the course of the study.

For those sites randomised to the DSS, there will be no patient intervention, but those sites will be trained on a DSS tool. The DSS is available in a web application that can be accessed on the Internet using the most common Web browsers, namely Google Chrome, Safari, Internet Explorer, Microsoft Edge, or Mozilla Firefox intended for clinicians to estimate the clinical benefit of any LLT regimen, whether monotherapy or combination therapies. The DSS does not recommend treatments but shows the expected ASCVD risk, absolute and relative ASCVD risk reductions and number needed to treat for the various treatments selected by the clinical user on the potential value of initiation of an add-on therapy for reducing the risk of recurrent cardiovascular (CV) events. Implementing the patient-specific recommendation remains at the clinicians' discretion. The DSS will be protected from unwanted use by asking its users to enter their OpenClinica credentials.

4.3. Study Population

Patients will be identified at hospitals that routinely manage and care for adults with ACS. Adults admitted with ACS to hospital sites where subsequent follow up of the patients is also carried out.

4.4. Eligibility Criteria

4.4.1. Inclusion Criteria

Sites which:

Imperial Clinical Trials Unit	ZODIAC STATISTICAL ANALYSIS PLAN – MAIN ANALYSIS	V1 17 th Jan 2024
-------------------------------	--	------------------------------

- Manage ACS patients as defined by: Symptoms of myocardial ischemia with an unstable pattern, occurring at rest or with minimal exertion, within 72 hours of an unscheduled hospital admission due to presumed or proven obstructive coronary disease and at least one of the following:
 - Elevated cardiac biomarkers
 - Resting electrocardiographic changes consistent with ischemia or infarction, plus additional evidence of obstructive coronary disease from regional wall motion or perfusion abnormality, 70% or more epicardial coronary stenosis by angiography, or need for coronary revascularization procedure
- Manage post ACS follow up care of patients including risk factor control
- Can provide follow up information on patient care for a maximum of 16 weeks including blood tests
- Are willing/ able to access and undertake training for the DSS
- Have adequate internet connection at site and the ability to access the DSS
- Have no restrictions on use of LLT (within national guidelines/ reimbursement)
- Collect patient information essential for DSS input on all of the following:
 - LDL-C, TC, HDL-C measurements.
 - Record of corresponding lipid-lowering therapy at the time the LDL-C is measured.
 - Estimated glomerular filtration rate (eGFR), e.g. available or derived using Modification of Diet in Renal Disease (MDRD)², or its component, the serum creatinine.
 - Patient's demographics (age, gender), clinical history (ASCVD, coronary artery disease, cerebrovascular disease, abdominal aortic aneurysm, peripheral artery disease, diabetes melitus), systolic blood pressure, smoking status.

Patients who:

- Are aged ≥ 18 to < 80 years old
- Can provide written informed consent
- Present to a study site with ACS as LLT naïve, monotherapy or combination therapy (defined as more than one LLT agent)
- Are willing to take LLT for the secondary prevention of CV disease
 - Attending the same study site (or same clinical team) for ACS follow up to ensure follow up data can be collected; or ensure that follow up data can be collected from other clinical institutions as part of the clinical pathway (patients are required to provide consent for the site to contact other health providers such as the patient's GP to collect relevant follow up information for the purposes of the study).

Imperial Clinical Trials Unit	ZODIAC STATISTICAL ANALYSIS PLAN – MAIN ANALYSIS	V1 17 th Jan 2024
-------------------------------	--	------------------------------

4.4.2. Exclusion Criteria:

Sites which:

- Are unable to capture/provide data on patients with ACS during admission and follow up (or are unable to facilitate follow up with e.g. the patient's GP where required for the purposes of the study)
- Are unable or unwilling to use LLT other than statins for ACS care

Patients who:

- Cannot provide written informed consent
- Have LDL-C measurement < 1.8 mmol/L at admission

4.5. Sample Size

It is estimated that in the SoC arm, we expect 7% of patients to be on combined therapy at 24 weeks. This estimate is based on published data (Koskinas et al³) using the ELIPS study cohort which included exclusively ACS patients. A slightly lower proportion of patients (5%) may be expected to be on combination therapy at 16 weeks.

To detect a meaningful difference in proportions from the SoC group of 0.05 to 0.15 in the DSS with 90% power, we require 744 patients in 24 clusters within each arm.

This calculation assumes a two-sided statistical test at the 5% significance level, ICC of 0.1 and clusters of a similar size (31 for each site).

Justification for ICC of 0.1: Based on the article by Campbell et al.⁴, it would be reasonable for a guideline implementation study within primary care to assume an ICC of the order of 0.1 for process variables and an ICC of less than 0.05 for the outcome variable. This is also in line with empirical estimates obtained from an online database with ICC reported for cluster studies that aimed to change practice.⁵ In the database we examined the hypertension guideline interventions, these varied from 0.048 to 0.064. In addition, we have to consider clustering within country; to be conservative we have assumed an ICC of 0.1.

Based on our experience working in this setting we do not expect any loss of clusters. However, drop out may occur within clusters. As data are extracted from routinely collected electronic healthcare records, we expect missing data to be low as it will only be patients who actively request data collection to stop that will have missing outcome data. Considering a conservative approach⁶ and assuming a loss to follow-up rate of 5%, we need a minimum total sample size of 1568. Considering adjusted numbers per cluster we aim to recruit 792 over 24 clusters per arm (a total sample size of 1584).

Imperial Clinical Trials Unit	ZODIAC STATISTICAL ANALYSIS PLAN – MAIN ANALYSIS	V1 17 th Jan 2024
----------------------------------	--	------------------------------

All calculations were done using PASS 2022 software⁷ and applying a method of “Tests for Two Proportions in a Cluster-Randomised Design”.

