14.1 Sample GP Letter

Study Letter: Implementation of a Decision Support System and its effect on early optimisation of Lipid-Lowering Therapies in patients with Acute Coronary Syndrome: a cluster Randomised Controlled Trial

(insert date)

Dr. (insert GP name)

(insert GP address and contact details)

Dear Dr. (insert GP name),

Participant Name:

DOB:

Address:

RE: OptimiZation Of lipid lowering therapies using a Decision support system In patients with Acute Coronary syndrome (ZODIAC). REC Ref: 22/SS/0106/ IRAS Ref: 317589

I am writing to inform you that your patient named above has consented to participate in the above-named study, sponsored by Imperial College London.

Imperial College London has developed a Decision Support System (DSS) which is a web app available online intended for clinicians to estimate the clinical benefit and risk over time of Lipid Lowering Treatment regimens, whether single or combination therapies. Your patient has been invited to join as they are an adult (up to 80 years of age) with ACS who has recently been hospitalised (within 72 hours).

The aim of this study is to assess whether the availability of the DSS compared to routine care alone results in an increased initiation or intensification of combination LLTs over a 16-week period after an ACS event. This is a cluster randomised trial with a total of 48 hospital sites across the UK, Spain and Italy– 24 DSS sites and 24 non DSS sites. DSS sites will receive a standardised period of training; following the DSS use it is still up to the clinician to choose & prescribe a suitable therapy for the patient.

The participant will be followed up after the study Baseline Visit (i.e. post-ACS event) over a 4 month period as per routine care and study data will be captured accordingly. Aside from participant consent, there are no other participant study procedures.

This study has been approved by the relevant Ethics Committees and Regulatory authorities and will be conducted in accordance with Good Clinical Practice and appropriate regulatory requirements.

Please find enclosed a participant information sheet which provides more details about the study and what it involves for your patient. If you would like further information about the study, please do not hesitate to contact me.

[figure not shown]
Thank you in advance for your co-operation.

Kind Regards,

XXX

ZODIAC	Imperial College London	V.3 17 JAN 24
--------	-------------------------	---------------

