3.1. Primary Objectives

To compare implementation of a DSS (aligned to the 2019 EAS/ESC Guidelines¹) added to routine clinical care as compared with routine care without a DSS, to assess whether the addition of a DSS system to current practice increases the likelihood of intensification of LLT defined as escalation of monotherapy, initiation of combination therapy or escalation of combination therapy within a 16-week period.

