5.2. Primary Efficacy Variable

Proportion of patients with intensification of LLT relative to baseline, regardless of adherence to the DSS, within 16 weeks of index ACS event.

Intensification includes:

- escalation of monotherapy OR
- initiation of combination therapy OR
- escalation of combination therapy

Only commercially available licensed LLT will be considered.

Patients will be considered LLT-naïve on admission if no LLT medications (statins, ezetimibe, bempedoic acid, bile acid sequestrants, evolocumab, alirocumab and inclisiran) are listed on the LLT 'prior to admission' form which captures LLT therapy in the month prior to admission. Patients who are admitted on medicines such as fish oils, nicotinic acid derivatives and fibrates will be considered to be a subgroup of LLT-naïve patients since these agents do not have a clinically significant effect on LDL levels.

Patients who are LLT-naïve on admission will be expected to start on statin monotherapy prior to discharge or an alternative monotherapy prior to discharge, and rarely post-discharge i.e. during follow up. For patients initiated on monotherapy as their first LLT, intensification of therapy in these patients can only occur after starting monotherapy. Therefore, the primary outcome will be met in these patients if they subsequently receive escalation of their monotherapy or start combination therapy during follow up. It is also possible that some LLT-naïve patients may be started on combination therapy at discharge. In this case the primary outcome will be met at discharge.

For patients who are already prescribed LLT prior to admission, they will meet the primary outcome if intensification occurs between admission and discharge or after discharge.

Table 2: Primary outcome definition

Baseline therapy patients recruited with	Meets primary outcome at 16 weeks if the patients is now on
<2 LLT drugs (i.e. 0 to 1)	Combination therapy (2 or more drugs) OR
	Escalated monotherapy (one drug increase in dose, or switch to more potent single drug)

Imperial Clinical Trials Unit	ZODIAC STATISTICAL ANALYSIS PLAN – MAIN ANALYSIS	V1 17 th Jan 2024
-------------------------------	--	------------------------------

>=2 LLT drugs	Escalated combination therapy (e.g. 3 drugs, increase in the potency of one of the drugs if the total number of drugs remains unchanged)
---------------	--

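### The 90% power in SAP 4.5 is calculated for being on combination therapy at 16 weeks; no power is stated for the primary outcome, which is any LLT intensification within 16 weeks

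*SAP*

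**What the plan says.** **Sample size (SAP 4.5).** The control rate starts from published data on acute coronary syndrome patients: "we expect 7% of patients to be on combined therapy at 24 weeks". It is then lowered: "A slightly lower proportion of patients (5%) may be expected to be on combination therapy at 16 weeks". The target is set from that rate: "To detect a meaningful difference in proportions from the SoC group of 0.05 to 0.15 in the DSS with 90% power", for which "we require 744 patients in 24 clusters within each arm". The remaining inputs are given as "This calculation assumes a two-sided statistical test at the 5% significance level, ICC of 0.1 and clusters of a similar size (31 for each site"). After 5% loss the minimum is 1568 in total, and the recruitment target is 1584.

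**Primary outcome.** SAP 3.1 defines it as "intensification of LLT defined as escalation of monotherapy, initiation of combination therapy or escalation of combination therapy within a 16-week period". SAP 5.2 repeats this as "Proportion of patients with intensification of LLT relative to baseline, regardless of adherence to the DSS, within 16 weeks of index ACS event" and says a patient counts if any of the three types occurs at any point in follow-up. The estimand in 6.1 and the analysis in 8.4 use the same composite.

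**Combination therapy alone** is a secondary variable (SAP 5.3, item 8), worded as receiving it by Week 16.

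The model legends in 8.4 and 8.8 nevertheless describe the modelled probability as that of combination therapy.

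**The concern.** The quantity that was powered and the quantity that will be tested differ in two ways.

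- **Type of event.** The 5% covers combination therapy only. The primary outcome also counts escalated monotherapy and escalated combination therapy.
- **Timing.** The 5% is a prevalence at 16 weeks. The outcome is an event at any time up to 16 weeks.

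The control rate of the composite is probably above 5%. One dose increase or a switch to a more potent single drug is enough (5.2, Table 2). Patients already on treatment can qualify between admission and discharge (5.2). Patients with LDL-C below 1.8 mmol/L at admission are excluded (4.4.2), so everyone enrolled starts above the 1.4 mmol/L target.

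The control rate matters because the binomial variance grows as the rate moves from 5% towards 50%. A fixed absolute difference then becomes harder to detect. A null primary result could be read against a 90% figure that belongs to another endpoint.

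**Working it through.** **Inputs (SAP 4.5).** 24 sites per arm, 31 patients per site, ICC 0.1, two-sided 5% level, 5% vs 15%, 90% power, 5% loss.

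**Step 1: reproduce the plan.**
- Design effect = 1 + (31 − 1) × 0.1 = 4.
- Unadjusted n per arm = (1.960 + 1.282)² × (0.05 × 0.95 + 0.15 × 0.85) / 0.10² = 183.9.
- 183.9 × 4 = 735.5; 735.5 / 31 = 23.7, so 24 sites; 24 × 31 = 744 per arm.
- Loss: 744 / 0.95 = 783.2, so 784 per arm and 1568 in total.
- By site: 31 / 0.95 = 32.6, so 33; 33 × 24 = 792 per arm and 1584 in total.

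All the stated figures are recovered.

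**Step 2: power at the planned size.** Effective n per arm = 744 / 4 = 186.

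Power = Φ( |p1 − p0| / √[(p0q0 + p1q1) / 186] − 1.96 )

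For 5% vs 15%: √(0.175 / 186) = 0.0307; 0.10 / 0.0307 = 3.26; Φ(1.30) = 0.903. With a pooled variance it is 0.898, and with a t reference on 46 df it is 0.891.

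**Step 3: the same formula at other control rates.** The documents do not give the control rate of the composite, so 10–50% is an assumed range. For ICC 0.05 the design effect is 2.5 and the effective n is 744 / 2.5 = 297.6. For ICC 0.15 they are 5.5 and 135.3. The detectable difference is the gap at which the formula returns 0.90, solved numerically.

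| Control rate | p0q0 + p1q1 at +10 points | Power, +10 points, ICC 0.1 | 90%-detectable difference, ICC 0.1 (risk ratio) | Power, +10 points, ICC 0.05 | Power, +10 points, ICC 0.15 |
|---|---|---|---|---|---|
| 5% (plan) | 0.175 | 0.90 | 9.9 points (2.99) | 0.98 | 0.79 |
| 10% | 0.250 | 0.78 | 12.2 (2.22) | 0.93 | 0.64 |
| 20% | 0.370 | 0.61 | 14.8 (1.74) | 0.81 | 0.48 |
| 30% | 0.450 | 0.53 | 16.1 (1.54) | 0.73 | 0.41 |
| 40% | 0.490 | 0.50 | 16.6 (1.41) | 0.69 | 0.38 |
| 50% | 0.490 | 0.50 | 16.4 (1.33) | 0.69 | 0.38 |

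**Step 4: larger effects, ICC 0.1.** 10% vs 25% gives 0.97; 20% vs 35% gives 0.91; 30% vs 50% gives 0.98. If the planned ratio of 3 held at control rates of 10–30%, power would exceed 0.99.

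**Step 5: unequal sites.** For 5% vs 15% with an assumed coefficient of variation of site size of 0.5, the design effect is 1 + (1.25 × 31 − 1) × 0.1 = 4.775. The effective n is 744 / 4.775 = 155.8 and power is 0.85.

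**The case against.** The strongest reply is that a mismatch of endpoint is not a shortage of power. A reader might infer from the table that the real power is near one half. That needs two things the documents do not supply: a control rate of about 30–50%, and an effect held at exactly 10 points. A wider outcome may carry a larger absolute effect, and the planned summary is a risk ratio. SAP 4.5 also reports empirical ICCs of 0.048 to 0.064 and calls 0.1 conservative. This part of the reply stands.

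A reader might also infer that the composite rate must exceed 5%. That does not follow strictly. The 5% is a prevalence and may include patients admitted on a combination and left unchanged, who do not count. Under 5.2, an LLT-naïve patient who only starts monotherapy does not count either. A higher rate is probable but not proven.

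A third tempting inference is that the outcome was widened and the sample size left behind. The legends in 8.4 and 8.8 would fit that, but no supplied record shows it. The sample GP letter is weak evidence, since it already speaks of a DSS that "results in an increased initiation or intensification of combination LLTs over a 16-week period after an ACS event". The protocol text available here contains no endpoint or sample-size section, so a justification given there could not be seen.

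Finally, the result will be reported with a 95% confidence interval, which shows the precision achieved whatever was planned. That limits the harm, but it does not make the 90% the power of the primary test.

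**Conclusion.** The point holds as a mismatch between endpoint and assumption. It is not an arithmetic error. The stated 90% belongs to being on combination therapy at 16 weeks; the power of the primary composite is not stated.

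Its size depends on what is assumed. At ICC 0.1 and a 10-point gain, power falls from 0.90 to between 0.78 and 0.50 over assumed control rates of 10–50%. Equivalently, the difference detectable with 90% power rises from 9.9 points to between 12.2 and 16.6. At ICC 0.05 the power range is 0.93 to 0.69. The documents do not support the conclusion that the trial is underpowered, because neither the control rate nor the expected effect on the composite is given.

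**What to change.** 1. In SAP 4.5, state that 5% vs 15% with 90% power refers to being on combination therapy at 16 weeks and not to the primary composite. Add that it only approximates secondary variable 8, which counts patients who received combination therapy by Week 16, with an overlap of at least one day.
2. Add a table for the primary composite showing power and the 90%-detectable difference, both absolute and as a risk ratio. Cover control rates of 10–50%, ICC 0.05, 0.1 and 0.15, and equal and unequal site sizes.
3. The blinded pooled event rate from the algorithm check at 25% recruitment (5.2) may be used to narrow the range. Note that it mixes both arms and is not the control rate, so a range must remain.
4. Correct the legends in 8.4 and 8.8 so that the modelled probability is that of the composite.

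The cost is a wording change and one short table. The stated power may look less favourable. Enrolment, outcome definition and analysis do not change.

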4.6. Randomisation

The 48 sites will be randomly assigned to DSS or SoC using permuted block randomisation stratified by country and site type (secondary/ tertiary care/mix of both). A randomisation list will be created by the Data Manager, and allocation concealment will be achieved using a secure local system.

Sites will only be randomised after being recruited by linking sites to a pre-randomised numeric list and stored in a secure web-based system.

The randomisation list is concealed from members of the team who are involved in recruitment. Concealment from the operational staff after randomisation has occurred is not possible but intervention allocation will be blinded to the patient.

The process is summarised in Figure 2.

[figure not shown]

Figure 2: Randomisation workflow

Imperial Clinical Trials Unit	ZODIAC STATISTICAL ANALYSIS PLAN – MAIN ANALYSIS	V1 17 th Jan 2024
-------------------------------	--	------------------------------

4.7. Blinding

Study patients and the analysing statistician will be blinded to the treatment group. Due to the nature of the intervention the study team delivering the intervention will not be blinded.

4.8. Follow Up

Follow-up clinic visits will take place as per routine clinical practice. In general these vary but are expected to occur within 3 months for patients accessing cardiac rehabilitation services or at approximately 12 weeks and 16 weeks post index ACS event after discharge in general (1-2 visits). We have not mandated additional visits and the follow up is intended to reflect routine care pathways although the exact timing may vary (maximum 16 weeks). These visits will consist of standard routine care in both randomised groups, with the exception that at DSS sites, staff will be asked to utilise the DSS to assess whether LLT should be further optimised for consented patients.

Routine clinical care includes blood tests for lipids and blood pressure evaluation, evaluation of lifestyle factors such as smoking, exercise, and diet. In the scenario that a cholesterol measurement is unavailable at the time of follow up, patients will be required to have blood tests after the routine follow up. This situation is not specific to this trial and reflects real world clinical practice.

Every effort will be made to ensure follow up data are collected by sites. Where follow up visits have not been attended by Week 16, sites will access the patient's local medical record and/or contact the patient's GP to determine the outcome data status at Week 16. In the event that the local medical record is not available or the GP does not respond, then the patient will be regarded as lost to follow up from the date of the last visit attended or last known prescription from the patient's record for the purposes of censoring.

Note that, for operational reasons, some patients may have data reported at 24 weeks only. These data may be used, where appropriate, to derive or impute the LLT medication status at 16 weeks.

The schedule of events is shown in **Error! Reference source not found..**

Table 1: Schedule of Time and Events

	Baseline	All other visits as per routine care up to 16 weeks
Visit	1	2 onwards
Informed consent	X	
Inclusion & exclusion criteria	X	X
DSS variables	X	X ^a
Demography	X	
CV Medical history	X	
Vital Signs ^b	X	X
Full Lipid Profile	X	X
Medications / LLT	X	X
Lifestyle (smoking, exercise & diet)	X	X
CV events	X	X

^a DSS use optional after Baseline visit

^b Includes height, weight, body mass index, temperature, diastolic and systolic blood pressure, and blood pressure position

5. Variables of Analysis

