We define the primary outcome as missing for anyone who does not have full 16 week follow up, unless they have met the primary outcome prior to the time they are lost to follow up. All patients will be followed up and the primary outcome data will be collected unless the participant requests to withdraw from data collection. Missing data will be examined and quantified; this will include the time of withdrawal and tabulation for reasons for non-completion of study by country, site, and arms. Patterns of missingness and relationship between variables and outcome will be explored. The proportion of clusters (sites) with a missing individual outcome will be calculated and reported as the number of entire clusters with a missing outcome divided by the number of clusters randomised.

As mentioned in Section 4.8, some patients may have data reported at 24 weeks only. These data may be used, where appropriate, to derive or impute the LLT medication status at 16 weeks.

Although mixed models are valid under the missing at random (MAR) assumption, we will use the multilevel multiple imputation (MMI) method to impute values for individuals who have missing outcome data. Missing data can be related to the cluster level or at patient level. We define level 1 variables as those relating to the patient as X and Y and Z, and level 2 variables as those relating to the site as A and B.

Using the *JOMO package* in R with missing outcome data we can use an imputation model which is the same as the analysis model. The JOMO package allows imputation on a mix of multilevel continuous and categorical data.¹⁵ This method uses Markov chain Monte Carlo (MCMC) methods to impute missing values. We will run N imputations and combine the estimates using the mitools package. We will impute N datasets based on the percentage of participants with incomplete outcomes, where N is rounded to the nearest 10. A minimum of 5 imputation datasets will be used. We will include at patient level, intervention, outcome,

Imperial Clinical Trials Unit	ZODIAC STATISTICAL ANALYSIS PLAN – MAIN ANALYSIS	V1 17 th Jan 2024
-------------------------------	--	------------------------------

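### The week-16 record check is tied to missed visits, so a patient seen once at about 12 weeks can count as a success if intensified but be set to missing if not

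*SAP*

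**What the plan says.** SAP 4.8 leaves follow-up to routine care. Visits are expected within 3 months for patients in cardiac rehabilitation, or at "approximately 12 weeks and 16 weeks post index ACS event after discharge in general (1-2 visits"). None is mandated and no visit window is given. The only stated trigger for going to the records is non-attendance: "Where follow up visits have not been attended by Week 16, sites will access" the local record, contact the GP, or both.

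The endpoint in 5.2 is intensification "within 16 weeks of index ACS event". For incomplete follow-up, 8.4 says: "We define the primary outcome as missing for anyone who does not have full 16 week follow up", with an exception for patients who had already met the outcome. Section 5.2 reads differently: a patient is *No* when therapy is unchanged or reduced for as long as follow-up lasts, and it does not require follow-up to reach week 16.

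Other sections promise more than 4.8 instructs. Section 4.5 describes extraction from electronic health records and expects missing outcomes only in patients who ask for collection to stop. Section 8.4 repeats that the outcome will be collected unless the patient withdraws from data collection. Section 4.1 adds that "all outcomes will be assessed as close to 16 weeks as possible". Sections 4.8 and 8.4 also let data reported only at 24 weeks be used to derive or impute week-16 therapy, without a rule for doing so.

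**The concern.** A patient whose only routine visit was at about 12 weeks has attended. Read as written, 4.8 does not send the site to the record for weeks 12 to 16, and no other operating instruction does so. The plan then treats two such patients differently. One intensified by week 12 is a known success. One not intensified by then lacks full follow-up and becomes missing under 8.4, even if the prescribing record would show no change to week 16.

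That rule is one-sided: it keeps events and loses non-events. Imputation would repair it only if the model used what was known at last contact. The listed variables (arm, outcome, age, sex, diabetes, time since first CV diagnosis, site type, country) do not include it, so missing patients are filled in from a pool in which events are over-represented. Intensification would be overstated in both arms. The risk ratio would be distorted most if the share last seen early differs by arm. Staff are unblinded (4.7), and DSS sites are asked to use the tool at follow-up visits (4.8), so a difference in visit timing is possible. The documents do not show that one exists.

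**Working it through.** **The plan's own figure.** Inputs from SAP 4.5: 0.05 versus 0.15, two-sided 5%, 90% power, ICC 0.1, 31 per site, 24 sites per arm, 5% loss.

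- Without clustering: n = (1.960 + 1.282)² × (0.05×0.95 + 0.15×0.85) / 0.10² = 183.9 per arm.
- Design effect = 1 + (31 − 1)×0.1 = 4.0, and 183.9 × 4 = 735.5. Dividing by 31 gives 23.7, so 24 clusters and 744 per arm.
- 744/0.95 = 783.2, so 784 per arm and 1568 in total. 31/0.95 = 32.6, so 33 per site, 792 per arm and 1584 in total.

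All stated figures reproduce.

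**One patient under each section.** Take a patient last seen at week 12 and not intensified by then.

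- 4.8: attended, so the record check is not clearly triggered.
- 4.5 and 8.4: the outcome is expected to be collected anyway.
- 8.4, definition of missing: missing, then imputed.
- 5.2, classification rule: can be read as *No*.
- 8.5.3 and 8.10: outside the secondary binary analyses and the complete-case analysis.

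**If the patient is set to missing.** Assume a share m of non-events goes missing, all events are kept, and imputation reproduces the observed proportion within each arm. The estimated proportion is then p* = p / [p + (1 − p)(1 − m)].

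| True SoC / DSS | m in SoC / DSS | p* in SoC | p* in DSS | Risk ratio (true value) |
|---|---|---|---|---|
| 5% / 15% | 30% / 30% | 0.05/0.715 = 7.0% | 0.15/0.745 = 20.1% | 2.88 (3.0) |
| 5% / 15% | 10% / 30% | 0.05/0.905 = 5.5% | 20.1% | 3.64 (3.0) |
| 5% / 15% | 30% / 10% | 7.0% | 0.15/0.915 = 16.4% | 2.34 (3.0) |
| 10% / 10% | 10% / 30% | 0.10/0.91 = 11.0% | 0.10/0.73 = 13.7% | 1.25 (1.0) |

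For a given m these are upper-end distortions. Events in the unseen weeks would also be missing, which shrinks the bias. It disappears only if nobody last seen early had intensified before that contact.

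**If the patient is counted *No*.** Suppose a share f of intensifications falls in unseen weeks, so p becomes p(1 − f). The effective size per arm is 744/4 = 186.

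- f = 10% in both arms: 4.5% versus 13.5%, power 0.86.
- f = 30% in both arms: 3.5% versus 10.5%, power 0.76. The risk ratio stays 3.0 in both cases.
- f = 10% SoC, 30% DSS: 4.5% versus 10.5%, risk ratio 2.33, power 0.59.
- f = 30% SoC, 10% DSS: 3.5% versus 13.5%, risk ratio 3.86, power 0.94.

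The two readings therefore move the proportions in opposite directions.

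**If data were simply lost at random.** With 33 recruited per site, a share d missing and nothing recovered by imputation, cluster size is c = 33(1 − d) and effective size is 24c/[1 + (c − 1)×0.1]. For d = 10%, 30% and 50% this gives 184.2, 172.7 and 155.3, with power 0.90, 0.88 and 0.84. Loss of numbers alone is not the problem.

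**The case against.** The strongest reply is that the plan already covers this. Sections 4.5 and 8.4 promise record-based collection for all who do not withdraw, and the inclusion criteria in 4.4 require that follow-up data be obtainable, from the GP if needed. The phrase about visits not attended is plural, and its stated purpose is to establish week-16 status, so it could cover a missed 16-week visit after an attended 12-week one. Section 4.1 would let a visit shortly before week 16 serve as the week-16 assessment. Nothing shows that visit timing differs by arm, and Table 1 makes DSS use optional after baseline.

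Much of this stands. That attenders have unobserved weeks is a risk, not a documented fact, and differential timing is conjecture. But a general promise does not override the one instruction telling sites when to open the record, and sites should not have to guess which reading applies. Nor does it settle *No* versus missing.

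A reader might also infer that most 16-week visits fall outside the endpoint because they run from discharge. The documents do not support that: 4.8 places visits after the index event and caps follow-up at 16 weeks. Any percentage would need a length of stay and a spread of visit dates that the documents do not give.

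**Conclusion.** The point holds as a gap between sections with a plausible route to bias. It is a cheap improvement, not a design failure. The trigger in 4.8 is narrower than the collection promised in 4.5 and 8.4. The missing-data rule in 8.4 loses only patients not yet intensified, and the imputation model cannot correct for that. On assumed shares of 10% to 30% of non-events missing, the risk ratio could move from 3.0 to between 2.34 and 3.64, or from 1.0 to 1.25. The true share is unknown. The 5% and 15% are planning rates for combination therapy, not for the composite primary outcome. The protocol's follow-up section and the Appendix A algorithm could not be read here, and either may already contain the missing instruction.

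Two stronger readings do not hold. A reader might infer that these patients are wrongly excluded from the primary analysis. They are imputed there, and drop out only of the complete-case and secondary binary analyses. A reader might also take the sample-size statement "A slightly lower proportion of patients (5%) may be expected to be on combination therapy at 16 weeks", against 7% at 24 weeks, as the error from using 24-week reports. Those rates concern combination therapy, the provision covers only some patients, and its wording permits derivation from dated changes.

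**What to change.** In 4.8, replace the trigger. For every patient in both arms not already recorded as intensified, whether or not visits were attended, the site checks the prescribing record (or the GP) on or after day 112 (16 × 7) from the index event. It enters dated LLT starts, stops and dose changes up to that day. Then:

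- In 8.4, define this check as full 16-week follow-up, so a record unchanged to day 112 is *No* and not missing. Align 5.2 with it.
- Use the index event date as the single time origin for the primary outcome in 4.1, 4.8, 5.2 and 8.4.
- Use 24-week reports only through changes dated on or before day 112. Where a change is undated, set the outcome to missing and impute.

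The 16-week endpoint stays as it is. Extending the window past day 112 to catch late visits would change the endpoint and is not needed here.

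The cost is SAP and eCRF wording plus one look-up per patient not yet intensified, from records that 4.5 already names as the data source. On the planning rates that is about 792×0.95 + 792×0.85 = 1,426 look-ups, or roughly 30 at each of 48 sites. It would be fewer if the composite outcome is more common than combination therapy alone.
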